7.5.2 Secondary efficacy variables

7.5.2.1 Revised ALS Functional Rating Scale

The ALSFRS-R (Cedarbaum JM et al., 1999) includes 12 items: speech, salivation, swallowing, handwriting, cutting food and handling utensils, dressing and hygiene, turning in bed and adjusting sheets, walking, climbing stairs, dyspnea, orthopnea, and respiratory insufficiency. Each item will be scored from 0 to 4, with lower values indicating worse function. The variables derived will be the scores of the 12 separate items, the total scores of each subdomain (bulbar [items 1-3], fine motor [4-6], gross motor [7-9] and respiratory [10-12]) and the total score of ALSFRS-R.

Descriptive statistics will be reported by treatment group for all items in the scale, as well as each subdomain and the total scale at each study visit (original values, and change from baseline).

Slope of decline will be estimated for both treatment groups, using a random slope model for change from baseline. To facilitate comparison with the main study, the model will be adjusted for REFALS randomization strata, and include the baseline measurement as a covariate.

Further, time to decline from baseline in an ALSFRS-R respiratory domain score (items 10–12) will be described (see [7.5.2.2](#)).

To describe the study population, two additional variables will be derived from the ALSFRS-R:

King's clinical stage is a staging system used to measure the clinical progression of the ALS disease across body system regions. Staging is not directly collected as part of the study. Instead, King's clinical stage will be estimated from the ALSFRS-R as follows (Balendra, 2014):

1. Respiratory failure (Item 10 = 0 or Item 12 < 4) ⇒ Stage 4b
2. Nutritional failure (answered item 5b) ⇒ Stage 4a
3. For lower stages, count the number of regions involved:
 - a. Bulbar (any of items 1–3 < 4)
 - b. Upper limbs (either of items 4 and 5a < 4)
 - c. Lower limbs (item 8 < 4)

King's stage is used to describe disease progression status at baseline.

ALS progression rate at baseline will be calculated as the number of points missing from a full ALSFRS-R score (48) at baseline divided by the time (in months) between symptom onset and the baseline ALSFRS-R measurement.

7.5.2.2 Time-to-event endpoints

The following time-to-event secondary efficacy variables will be evaluated:

1. Time to NIV or death (NIVDEATH)
2. Time to decline from baseline in any ALSFRS-R respiratory domain score (FRSBR1D)

The data for the time-to-event variables will be stored in the ADTTE dataset with parameter names corresponding to those in parentheses above.

Premature discontinuations will be treated as right-censored in the analyses. Censoring rules for different scenarios are described in [Table 1](#). For the purpose of determining the end date, survival and ventilation status are considered to be assessed daily; ALSFRS-R and SVC measurements are assessed only on study visits.

For descriptive purposes, Kaplan-Meier survival curves will be plotted.

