8.4.3 Analysis of efficacy

Slope of decline in sitting and supine SVC and ALSFRS-R will be estimated using a random slope model. Estimation will be performed with and without the data collected in the REFALS study. When appropriate, between-subject comparisons will be performed using the randomised treatment arm in the REFALS study including a treatment-by-study interaction term.

Median time to NIV or death and to decline (by at least 1 point) in the ALSFRS-R respiratory domain will be evaluated using Kaplan-Meier estimates. Estimation will be performed with and without the data collected in the REFALS study. When appropriate, between-subject comparisons will be performed using the randomised treatment arm in the REFALS study, and Cox' proportional hazard regression model including treatment by study interaction term.

Borg CR10 (sitting, supine and orthostatic changes) will be evaluated using mixed model for repeated measures (MMRM) with and without the data collected in the REFALS study. When appropriate, between-subject comparisons will be performed using the randomised treatment arm in the REFALS study and appropriate MMRM including treatment by study interaction term.

Health and home care resource use data will be summarised in the study report, but any further analysis for potential pharmacoeconomic purposes will be reported separately.

To avoid selection bias in estimations, sensitivity analyses including all the subjects enrolled in the REFALS study will be considered. No imputation for missing data is planned. All efficacy data will be listed and summarised over time using appropriate descriptive statistics.

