7.5.2.3 Borg Category Ratio 10 Scale

The Borg Category Ratio 10 (CR10) scale will be used in the assessment of dyspnoea (Borg GA, 1982). The subjects will be asked to point out a score quantifying their perception on the intensity of dyspnoea on the CR10 scale at rest in sitting and supine positions (immediately before SVC measurements). Orthostatic changes between sitting and supine positions will be calculated.

Descriptive statistics for all Borg CR10 variables (original values, and change from baseline) will be reported by treatment group for each study visit.

Table 1. Censoring rules for time-to-event analyses.

Scenario	Censored	End date
Event criteria fulfilled	No	Date of endpoint assessment
Event criteria fulfilled at baseline	Yes	Date of baseline visit
Event criteria never assessed	Yes	Date of baseline visit
Discontinued study	Yes	Date of last endpoint assessment
Discontinued study treatment (1 day after*)	Yes	Date of last endpoint assessment
Died, when death not part of event criteria	Yes	Date of last endpoint assessment
Died, when death is part of event criteria	No	Date of death

*) to account for potential events following immediately after the study treatment discontinuation.

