7.10.4 Combined analyses with the main study

Additional analyses combining the data collected in REFALS with the data collected in REFALS-ES will be performed outside the scope of the clinical study report. This section outlines the currently planned analyses.

The primary population used for combined reporting will be the REFALS safety population.

REFALS study baseline characteristics will be reported for the REFALS-ES safety population.

Descriptive statistics for change from REFALS baseline will be reported for supine SVC, ALSFR-R and Borg endpoints, as well as vital signs (pulse rate, systolic and diastolic blood pressure).

Descriptive statistics for supine SVC and ALSFRS-R endpoints over the course of both studies will be reported in relevant efficacy subgroups identified in the REFALS study.

Random slope models will be fitted using data from both studies to estimate the rate of decline in supine SVC and ALSFRS-R endpoints over an extended follow-up period. A time-by-study-by-arm interaction will be investigated to potentially identify a change in slopes for the placebo arm transitioning over to active treatment for REFALS-ES.

Kaplan-Meier curves will be estimated for the time-to-event endpoints described in 7.5.2.2, and additionally time to invasive ventilation (tracheostomy or intubation) or death, and time to death. Estimation will start from the REFALS baseline and continue until the end of the extension study.

Adverse events and the number of deaths over the course of both studies will be summarised.

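### The Kaplan-Meier curve for respiratory-domain decline (FRSBR1D) censors deaths, so one minus that curve should not be read as the proportion of subjects who decline

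*SAP*

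**What the plan says.** SAP 7.5.2.2 lists two time-to-event endpoints: NIVDEATH (NIV or death) and FRSBR1D (decline from baseline in an ALSFRS-R respiratory score). On follow-up that ends early it says "Premature discontinuations will be treated as right-censored in the analyses". That sentence does not mention deaths. The rule for deaths is in SAP Table 1, in the row "Died, when death not part of event criteria": the subject is censored, with the last endpoint assessment as end date. The row applies to FRSBR1D. For NIVDEATH, Table 1 counts death as an event on the date of death.

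Decline can be seen only at contacts: "ALSFRS-R and SVC measurements are assessed only on study visits". Protocol 6.1.2 fixes contacts at 2 and 6 weeks and then allows up to 3 months between centre visits.

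The estimator is Kaplan-Meier. The SAP says "For descriptive purposes, Kaplan-Meier survival curves will be plotted", and protocol 8.4.3 says that the median time to "decline (by at least 1 point) in the ALSFRS-R respiratory domain will be evaluated using Kaplan-Meier estimates". SAP 7.10.4 takes the same endpoints into the combined analysis with REFALS, gives no other censoring rule, and says "Estimation will start from the REFALS baseline and continue until the end of the extension study".

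No second view of FRSBR1D is planned. SAP 6.2.4 gives no strategy for intercurrent events, 7.5.4 plans no sensitivity analysis, and neither a cumulative incidence curve nor a decline-or-death version appears.

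**The concern.** Kaplan-Meier treats a censored subject as someone who could still have the event, at the same rate as those who remain under observation. A subject who has died cannot decline later. The documents make death neither rare nor clearly unrelated to the endpoint: protocol 1.1 gives a median survival of about 3 years from symptom onset and describes loss of respiratory function as part of the disease.

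Two separate things then go wrong if 1-KM is read as the share of subjects who decline:

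- The weight of those who died is passed to survivors, which pushes 1-KM above the share in whom decline was observed.
- Subjects who decline after their last assessment and then die are censored as if they had not declined, which pushes the estimate below the share who truly declined.

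At stake is how a reader interprets the only time-to-event display of respiratory-domain decline, in the study report and over the longer follow-up of the combined analysis.

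**Working it through.** **Inputs.** The documents give no rate of decline, no mortality for this cohort and no figure to reproduce. All hazards below are assumptions. From the documents come the endpoint, the Table 1 rule, assessment at contacts only, and contacts at about 0.5 and 1.4 months and then every 3 months.

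**Step 1: gap against observed decline, constant independent hazards.** Let λ be the hazard of decline and μ the hazard of death among subjects who have *not yet declined*. Only those deaths are censored; after a recorded decline the event has already counted.

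- 1-KM = 1 − exp(−λt)
- Cumulative incidence with death competing = λ/(λ+μ) × [1 − exp(−(λ+μ)t)]
- Decline or death = 1 − exp(−(λ+μ)t)

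Take 1-KM = 60% at 12 months, so λ = −ln 0.4 = 0.916 per year, and μ = −ln(1 − m) for an assumed annual decline-free mortality m. For m = 10%, μ = 0.105 and the cumulative incidence is 0.916/1.022 × (1 − 0.36) = 57.4%.

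| m | Cumulative incidence | Gap to 1-KM (points) |
|---|---|---|
| 2% | 59.5% | 0.5 |
| 5% | 58.7% | 1.3 |
| 10% | 57.4% | 2.6 |
| 20% | 54.7% | 5.3 |
| 30% | 51.8% | 8.2 |

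With assumed median times to decline of 4 to 18 months and m of 5% to 30%, the gap is 0.9 to 9.6 points at 12 months and 0.3 to 4.5 points at 6 months. Including the 2% row, the 12-month range is about 0.5 to 10 points.

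The gap grows with follow-up. At 24 months with the same λ, 1-KM is 84.0%, against 82.8% for m = 2% and 78.1% for m = 10% (1.2 and 5.9 points).

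The effect on the median is small. With a median of 6 months and m = 10%, the cumulative incidence reaches 50% at about 6.2 months.

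**Step 2: direction against true decline.** The Table 1 rule was simulated with 400,000 subjects per scenario. Decline was seen only at visits, deaths were censored at the last visit, and the 12-month death risk differed before and after decline. Results at 12 months:

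| Median to decline (months) | Death risk before / after decline | 1-KM under the SAP | Observed decline (cumulative incidence) | True decline before death | Decline or death |
|---|---|---|---|---|---|
| 6 | 10% / 10% | 75.0% | 71.3% | 72.1% | 77.5% |
| 6 | 2% / 50% | 72.7% | 69.4% | 74.3% | 75.5% |
| 12 | 2% / 50% | 47.9% | 46.4% | 49.8% | 51.2% |

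When death is unrelated to decline (first row), 1-KM lies above true decline by 75.0 − 72.1 = 2.9 points. When death mostly follows decline (second and third rows), it lies below by 74.3 − 72.7 = 1.6 and 49.8 − 47.9 = 1.9 points. In every scenario computed it is above observed decline and below decline-or-death.

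**Step 3: what brackets the truth.** Everyone with observed decline truly declined before death, and everyone who truly declined before death is in the decline-or-death group. Observed cumulative incidence and decline-or-death are therefore a lower and an upper bound for true decline before death. In the second row they are 69.4% and 75.5%, around 74.3%.

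**The case against.** The strongest case for leaving the plan alone is that little depends on this curve. Safety is the primary objective, SAP sections 4 and 6.2.2 set no hypotheses or tests, and section 7.11 says that most statistical analyses were removed after the main study. The SAP promises survival curves and nowhere says that 1-KM will be reported as a proportion. Death is visible elsewhere: in NIVDEATH, in the table of deaths (7.9.1), and in the time-to-death curve of 7.10.4, which itself lies outside the study report. Table 1 separates composite from non-composite endpoints explicitly, so treating death differently for the two endpoints is a choice and not an internal contradiction. ALSFRS-R is also collected by telephone, and a caregiver may take the call (protocol 6.2.2 and 6.1.2), which limits missed decline. All of this stands, and it keeps the priority low. It does not make the FRSBR1D curve an estimate of the proportion declining, and a separate curve of deaths does not change how FRSBR1D reads.

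Two stronger readings are tempting and are not supported:

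- **That the plan necessarily overstates decline.** This is guaranteed only against the cumulative incidence of observed decline. The more closely death follows respiratory decline, the more the unrecorded decline pulls the other way.
- **That the comparison of prior treatment arms is distorted.** With independent hazards, a difference in mortality leaves the Kaplan-Meier curve for decline unchanged; it is the cumulative incidence that moves. Distortion of Kaplan-Meier needs dependence between death and decline that differs in effect between arms, and the documents give nothing from which to size that. Nor does the SAP plan a formal time-to-event comparison.

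A fair objection to the remedy is that Aalen-Johansen alone can lie further from true decline than Kaplan-Meier does (69.4% against 72.7%, truth 74.3%). That is why it should be paired with decline-or-death.

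**Conclusion.** The point holds as one of interpretation. Under Table 1, 1-KM for FRSBR1D is not the proportion of subjects who decline. It is at or above the cumulative incidence of observed decline, by about 0.5 to 10 points at 12 months under the assumed ranges. It may lie above or below true decline; the departures in the three scenarios shown are about 2 to 3 points in either direction.

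The size depends on mortality among subjects who have not yet declined and on how far death follows decline. The documents give neither. If most deaths come after recorded decline, the gap is near the low end. This is a low-priority improvement to a descriptive display.

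**What to change.** 1. In SAP 7.5.2.2, and for the combined curves in 7.10.4, add a decline-or-death version of FRSBR1D parallel to NIVDEATH. Amend Table 1 so that, for this version, death is an event on the date of death.
2. For FRSBR1D itself, report the Aalen-Johansen cumulative incidence of observed decline with death as a competing event.
3. State that decline between the last ALSFRS-R assessment and death is not observed, so that the two curves are read as a lower and an upper bound.
4. If the Kaplan-Meier curve is kept, label it as not estimating the proportion of subjects who decline.

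The cost is SAP wording, routine programming and one or two extra descriptive curves. Survival status is already collected at visits and telephone contacts, so no new data are needed. A median may not be reached on the cumulative incidence curve; the decline-or-death curve can supply one where it is reached.

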7.5.2.3 Borg Category Ratio 10 Scale

The Borg Category Ratio 10 (CR10) scale will be used in the assessment of dyspnoea (Borg GA, 1982). The subjects will be asked to point out a score quantifying their perception on the intensity of dyspnoea on the CR10 scale at rest in sitting and supine positions (immediately before SVC measurements). Orthostatic changes between sitting and supine positions will be calculated.

Descriptive statistics for all Borg CR10 variables (original values, and change from baseline) will be reported by treatment group for each study visit.

Table 1. Censoring rules for time-to-event analyses.

Scenario	Censored	End date
Event criteria fulfilled	No	Date of endpoint assessment
Event criteria fulfilled at baseline	Yes	Date of baseline visit
Event criteria never assessed	Yes	Date of baseline visit
Discontinued study	Yes	Date of last endpoint assessment
Discontinued study treatment (1 day after*)	Yes	Date of last endpoint assessment
Died, when death not part of event criteria	Yes	Date of last endpoint assessment
Died, when death is part of event criteria	No	Date of death

*) to account for potential events following immediately after the study treatment discontinuation.

7.5.3 Additional variables

7.5.3.1 Health care and home care resource use

The subjects will be given a home diary for recording their use of health and home care resources. The diary will be filled in on a weekly basis. Any hospital inpatient days, other institutional care, any additional hospital emergency unit visits, days in other institutional care, and any outpatient visits to physicians or other relevant service providers will be recorded. In addition, all non-medical assistive devices that the subjects have in use at baseline are recorded, and thereafter all new devices that they start using due to ALS will be recorded in the diary each week. Regarding home care, the diary will contain information of the number of formal (paid/public services) and informal (unpaid e.g. by spouse, other family members, friends or other volunteers) home care hours received. Additionally, information will be collected about the number of times such home care has been received during the nighttime. Details of the home diary will be described in a separate document.

Health and home care resource use data will be aggregated over the course of the study for each subject, and summarised using descriptive statistics. Any further analysis for potential pharmacoeconomic purposes will be reported separately.

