The study will continue at least until the time of marketing approval of oral levosimendan, cessation of development of oral levosimendan for ALS, or 3 years, whichever occurs first in each participating country. Continuation after this time will be at the discretion of the sponsor. On termination of the study, an appropriate method of continued treatment supply will be sought for any subjects still requiring treatment with oral levosimendan.

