2. OVERALL STUDY DESIGN AND PLAN

[figure not shown]
This is an open, non-randomised, uncontrolled, multicentre phase III extension study to the REFALS study.

The subjects will give informed consent (IC) to continue in this open-label extension study at the 48-week or end-of-study visit of the REFALS (or between these visits). The REFALS end-of-study visit will double as the REFALS-ES baseline visit. Visits to the study centre are flexible but occur at least every 3 months. Subject assessments will be conducted 2 weeks after starting the study treatment and after each change in the dose: such visits may be at study centre or conducted remotely where feasible (see section 6.1.3 in the protocol). A telephone contact will be performed for all subjects 6 weeks after starting the treatment.

The subject may continue the treatment as long as clinically indicated (see withdrawal criteria in section 4.5 in the protocol) or until the study ends.

An end-of-study visit will take place 14-25 days after the last study treatment administration for each subject.

The study design is presented in [Figure 1](#).

TC = telephone contact, EOS = end-of-study

¹ Dose increased to 1 mg b.i.d. if the 1 mg/day dosing was well tolerated

² Additional visit approx. 2 weeks after any dose change at visit 2

Figure 1. Study design

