7.1 Disposition of subjects

329 subjects completed the REFALS study. Of those, 28 were ineligible to continue to the extension study, and 54 otherwise eligible subjects did not wish to continue. Of the remaining 247 subjects who wished to continue, 20 were delayed due to COVID-19 related restrictions, and did not start the study before the recruitment was closed. In total, 227 subjects were screened and started the extension.

The number of subjects will be tabulated by treatment group for the following populations:

- Screened population
- Safety population
- Discontinued study

Separate tables by treatment group will also be provided for each country, and each study centre.

The disposition and number of subjects, along with reasons for screening failure and study discontinuations, will be listed and tabulated by treatment group.

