7.4 Extent of exposure and treatment compliance

The total number of exposed subjects, the total duration of study treatment exposure (continuous, and categorized both separately and cumulatively at the thresholds of ≤ 4 , ≤ 8 , ≤ 12 , ≤ 24 , and ≤ 48 weeks), and dose levels (in milligrams), averaged over the course of the study as well as at each study visit, will be reported as measures of extent of exposure.

Dose changes will be described by reporting the subject counts in the following categories:

- 1) remained at 1 mg for the entire study (“never increased”)
- 2) uptitrated to 2 mg and remained for the rest of the study (“increased and remained”)
- 3) uptitrated to 2 mg and later downtitrated to 1 mg (“increased, then decreased”)
- 4) downtitrated to 0.5 mg directly (“decreased directly”).

Treatment compliance will be described by reporting the number of dispensed and returned study treatment capsules at each study visit. The number of subjects with treatment interruptions longer than 7 days will be reported with descriptive statistics.

Both extent of exposure and treatment compliance will be tabulated with descriptive statistics.

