7.11 Changes from the clinical study protocol

Due to the results of the main study, and the consequent early termination of this extension study, the scope of reporting has been narrowed.

Most statistical analyses have been removed; instead, we report only descriptive statistics.

The analysis population is referred to as “safety population” rather than “full analysis set” for clarity, as the definition completely aligns with the safety population concept.

Protocol-defined reporting of REFALS baseline characteristics has been moved to additional analyses. Baseline characteristic reporting now reflects status at REFALS-ES baseline.

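### Resource use is aggregated over each subject's whole participation with no time denominator, so per-subject totals are confounded with unequal, truncated follow-up

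*SAP*

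**What the plan says.** SAP 7.5.3.1 lists resource use under additional variables. It covers inpatient and institutional days, emergency and outpatient visits, formal and informal home care hours, night-time care and new assistive devices. On collection it says "The diary will be filled in on a weekly basis". On analysis it says "Health and home care resource use data will be aggregated over the course of the study for each subject, and summarised using descriptive statistics", and it leaves any further pharmacoeconomic work to a separate report. Protocol 8.4.3 adds only that "Health and home care resource use data will be summarised in the study report". Neither text mentions a rate, a denominator or a fixed window.

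On follow-up, SAP section 2 says "The subject may continue the treatment as long as clinically indicated" or until the study ends. Protocol 1.2.1 says "The study will continue at least until the time of marketing approval of oral levosimendan", cessation of development for ALS, or 3 years, whichever comes first in each country. SAP 7.11 then refers to "the consequent early termination of this extension study". SAP 7.1 gives the size of the study: "In total, 227 subjects were screened and started the extension".

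**The concern.** Days, visits and hours of care accumulate with time. If subjects are observed for different lengths of time, a whole-study total is the product of two things: the rate of use and the time over which it was recorded. A subject who dies or stops early can have a low total despite heavy use. In a rapidly progressive disease, early exit may well go with heavy care needs, so the loss of follow-up may be informative.

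The SAP handles the same problem elsewhere. Section 7.9.2 gives adverse event incidence rates adjusted for exposure time, and section 7.5.2.2 censors the time-to-event endpoints. Resource use has no counterpart. SAP 7.5.4 plans no sensitivity analysis, and SAP 6.2.5 applies no missing-data handling.

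What is at stake is how the resource-use table in the study report is read. A reader could take low totals as low need, or take a difference in follow-up as a difference in use.

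**Working it through.** **Inputs from the documents.**
- Summary rule: whole-study aggregate per subject, no denominator (SAP 7.5.3.1; Protocol 8.4.3 is silent).
- Entry: the REFALS end-of-study visit doubles as baseline (Protocol section 3), so entry is staggered. Recruitment closed with 20 willing subjects still waiting (SAP 7.1).
- Exit: individual and open-ended, then cut short by early termination (SAP section 2 and 7.11).
- Month length: 30.4375 days (SAP 6.2.9).
- Observed follow-up and spread of use: not given. SAP 7.4 only plans to report exposure, with cut-points at 4, 8, 12, 24 and 48 weeks.

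The plan states no figure to reproduce on this point. All numbers below are illustrations with assumed values.

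**1. Can totals differ when use does not?** Total = rate × time. At 10 hours of home care per week for everyone, follow-up of 4, 12, 24 and 48 weeks gives 40, 120, 240 and 480 hours. That is a 12-fold spread with no difference in use. Divided by weeks observed, all four are 10 hours per week.

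**2. Can totals reverse the ranking?**
- Inpatient days: 13 weeks = 91/30.4375 = 2.99 months, so 4 days is 4/2.99 = 1.34 per month. 52 weeks = 364/30.4375 = 11.96 months, so 8 days is 8/11.96 = 0.67 per month. The subject with twice the rate shows half the total.
- Home care: 20 hours per week for 8 weeks totals 160 hours; 5 hours per week for 48 weeks totals 240 hours. The total again ranks the heavier user lower.

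**3. How much of the spread in totals would be due to follow-up?** Take rate and follow-up T as independent. The share of variance in totals due to follow-up alone is

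Var(T) / [Var(T) + CV² × E(T²)],

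where CV is the between-subject coefficient of variation of the weekly rate. For T uniform on 4 to 48 weeks, the mean is 26, Var(T) = 44²/12 = 161.3 and E(T²) = 161.3 + 26² = 837.3.

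| CV of weekly rate | Share due to follow-up |
|---|---|
| 0.25 | 75.5% |
| 0.5 | 43.5% |
| 1.0 | 16.2% |
| 1.5 | 7.9% |
| 2.0 | 4.6% |

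A simulation of 200,000 draws with gamma-distributed rates agreed to within 0.3 percentage points. Follow-up exceeds half the variance only if CV is below √(161.3/837.3) = 0.44. For T on 12–48, 4–72 and 4–96 weeks that break-even is 0.33, 0.46 and 0.47. At a CV of 1.0 the share is 9.7% to 18.0% over all four ranges.

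So totals are always contaminated by follow-up when follow-up varies, but whether follow-up dominates depends on quantities that the documents do not give.

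**The case against.** The case on the other side has several parts.

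- **The text does not forbid a denominator.** The SAP says the data are aggregated; it does not say raw totals, and it is silent on division by time. That is right, and the exact statement is that no denominator is specified. A single whole-study total per subject is nevertheless the natural reading.
- **By-visit tables may exist.** The opening rule of SAP 7.5 lists and tabulates all efficacy data by treatment group and visit, and Protocol 8.4.3 has efficacy data summarised over time. If this covers resource use, it helps in part. But 7.5.3.1 itself specifies only the whole-study aggregate, and visits are flexible with a minimum of one centre visit every 3 months, so amounts per visit would still cover unequal intervals.
- **Exposure is reported anyway.** SAP 7.4 reports "the total duration of study treatment exposure", both continuous and categorised. A reader could form a crude group ratio from it, but not a per-subject rate distribution, and treatment exposure is not the same as time with resource data.
- **Little depends on it.** There is no hypothesis or test, the primary objective is safety, and the reporting scope was deliberately narrowed (SAP 7.11). This stands and limits the importance of the point.

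A reader might also infer that totals mainly measure how long a subject stayed. The documents do not support that: on the assumptions above it fails unless weekly use is fairly homogeneous between subjects. Nor do they show that the comparison by prior arm is distorted. That would need follow-up to differ between the arms, or to relate differently to use in each, and no such data are given.

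**Conclusion.** The point holds as a confounding of totals with time observed. It rests on three things in the documents: a whole-study aggregate, no specified time denominator, and follow-up that is open-ended, staggered in entry and truncated by early termination. Reversal of individual rankings is shown to be possible by assumed examples only, and the actual size is unknown because neither the follow-up distribution nor the between-subject spread of use is available.

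This is more than a missing detail, because a rate would change the figures reported and what they mean. It is still a minor improvement to a descriptive additional variable.

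**What to change.** Add to SAP 7.5.3.1, for the accruing resources (inpatient and institutional days, emergency and outpatient visits, home care hours, night-time care):

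1. Report use per subject-month of resource-use observation: group total units divided by group total diary time with data.
2. Report the distribution of per-subject rates as well. The two summaries differ: in the home care example the pooled rate is 400/56 = 7.14 hours per week, while the individual rates are 20 and 5.
3. Show observation time beside each rate, and keep raw totals as a secondary line.
4. Report new assistive devices as counts or proportions, with observation time shown, since they are not naturally units per month.

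The denominator should be time with resource data, not time on study. Protocol Table 1 schedules no resource-use collection at the end-of-study visit, 14–25 days after the last dose, and SAP 6.2.5 does nothing about missing data, so counting unrecorded weeks would bias rates downward. The SAP should state the start and end of this period and how weeks without an entry are treated.

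The cost is a few sentences and one derived variable, which the weekly collection described in the SAP should supply. Per-subject rates are unstable when follow-up is very short, which the pooled rate largely avoids. A rate does not remove bias from informative early exit; it only stops short observation from appearing as low use.
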